A borderline statistically significant difference in 60-day all-cause mortality (primary endpoint) was found in the cohort where the subject was maintained for $\geq 90\%$ of the treatment in the protocol's recommended ionized calcium (riCa) target range of $\leq 0.40 \text{ mmol/L}$ over those that were maintained $\leq 90\%$ of the treatment duration.

The secondary endpoints of renal replacement therapy dependency at day 60, mortality at day 28, number of ventilator free days at day 28 and mortality of the sub population of severe septic subjects at day 60 were analyzed. No statistical significance was shown

except for the secondary endpoint of dialysis dependency. Dialysis dependency showed a statistically significant difference between the subjects maintained for $\geq 90\%$ of the treatment in the protocol's riCa target range of ≤ 0.40 mmol/L over those at $\leq 90\%$ of the treatment duration. See **Table 8**.

Table 8: Dialysis Dependency at Day 60 – Recommended Ionized Calcium Range

Dialysis Dependency at Day 60 riCa	CRRT + SCD	CRRT Alone
N	0/16	4/16
p-value		0.033

When a composite endpoint of all-cause mortality (primary endpoint) or renal replacement therapy dependency (a secondary endpoint) at day 60 is analyzed, a statistical significance is observed. See **Table 9**.

Table 9: 60 Day Combined End Point of All-Cause Mortality or Dialysis Dependency – Recommended Ionized Calcium Range

60 Day Combined End Point of All-Cause Mortality or Dialysis Dependency -- riCa	CRRT + SCD N=19	CRRT Alone N=27
	15.8%	55.6%
N	3/19	15/27
p-value		0.007

2.5.4 CONCLUSION AT INTERIM ANALYSIS

The SCD-003 Protocol included one formal interim effectiveness analysis on the primary endpoint of time to all-cause mortality by 60 days for review by the DSMB. On September 3, 2013, CytoPherx (now SeaStar Medical) received concurrence from the DSMB that they would have recommended continuing the SCD-003 study (with appropriate corrective action to ensure the protocol's riCa target range of < 0.40 mmol/L be maintained). However, due to the existing statistical deficit, an increase in sample size to achieve a statistically significant treatment difference on the primary endpoint would have been required. This increase in sample size would be prohibitive for CytoPherx (now SeaStar Medical) to finance.

Rather than continue SCD-003, SeaStar terminated the study and intends to submit to FDA a supplement to IDE [REDACTED] for

approval of a new clinical trial protocol (no changes to the SCD device) designed to achieve statistical significance of a death or dialysis dependence composite endpoint.

2.6 Clinical Study: SCD-PED-001 (Pilot Safety and Efficacy of SCD treatment in Pediatric Patients with AKI) IDE [REDACTED]

This was a single treatment arm, open-label multi-center pilot study, grant funded by the FDA, designed to enroll 16 subjects across 4 clinical sites in the United States. The study assessed the safety of the SCD and outcomes in pediatric patients (>15 kg, ≤22 years) with AKI and multiorgan failure receiving CRRT. Sixteen subjects were enrolled between December 2016 and January 2020. In these subjects, the SCD was integrated post CRRT membrane, changed daily, and circuit ionized (i)Ca maintained <0.4 mmol/L. Subjects received SCD treatment for up to 7 days or CRRT discontinuation.

2.8 Ongoing SCD Trials

2.8.1 Investigator Initiated Feasibility Study: “Immunomodulatory Biomimetic Device to Treat Myocardial Stunning in ESRD Patients”

- IDE [REDACTED], IRB approved
- 10 subjects, single site, one 4 hours SCD treatment in chronic hemodialysis patients with recurrent hemodialysis hypotension due to rapid large volume removal rates.
- SCD treatment vs. control treatment in same subject; myocardial ischemia as measured with Echocardiogram.
- If effective, reduce chronic heart failure progression (5-10% ejection fraction loss annually).

2.8.2 Investigator Initiated Pilot Study to Assess the Safety and Efficacy of a Selective Cytopheretic Device (SCD) to Treat ICU Patients with Acute on Chronic Systolic Heart Failure with Cardiorenal Syndrome Awaiting Left Ventricular Assist Device (LVAD) Implantation or Diuretic Resistant (2 clinical protocols)

- IDE [REDACTED]; IRB approved
- 10 subjects, single site, non-control trial. Stage 4 CHF patients with worsening renal function from CRS are not eligible for LVAD.
- Daily 6 hour SCD treatment (up to 7 days) to assess improvement in renal function and LV systolic function to become eligible for LVAD implantation.
- Positive efficacy study would be proof of concept of SCD effects to improve LV function and renal function.
- Recent Supplement to include CRS diuretic resistant patients requiring ultrafiltration: 3 treatments during 4 hour UF treatments.

2.8.3 Investigator Initiated Pilot Study to Assess the Safety and Efficacy of a Selective Cytopheretic Device (SCD) to Treat ICU Patients with Acute Kidney Injury (AKI) and Hepatorenal Syndrome (HRS) Type I

- IDE [REDACTED], IRB approved
- 10 subjects, single site trial in ICU patients with AKI and HRS not on liver transplant list. Prognosis is 80 percent mortality in 90 days.
- Daily 24 hour SCD treatment up to 7 days to assess improvement in renal function and volume removal.

2.8.4 A Multi-Center Pilot Study to Assess the Safety and Efficacy of a Selective Cytopheretic Device (SCD) in Patients Developing Acute Kidney Injury (AKI) or Acute Respiratory Distress Syndrome (ARDS) Associated with COVID-19 Infection (Sponsor: SeaStar Medical)

- IDE [REDACTED] S34; IRB approved

- 35 subjects, up to 10 clinical sites, treatment arm only, ICU patients with COVID 19 with ARDS and/or AKI requiring CRRT.
- Daily 24 hour SCD treatment up to 10 days to assess safety and efficacy on 60 day mortality and renal recovery.

3. STUDY OBJECTIVES AND ENDPOINTS

3.1 PRIMARY OBJECTIVE

To evaluate the safety of up to ten consecutive 24 hour SCD treatments compared to historic data on in-hospital mortality and on all-cause mortality and dialysis dependency at day 28, and day 60 in the pediatric AKI population being treated with Continuous Renal Replacement Therapy (CVVH, CVVHD, or CVVHDF) with regional citrate anticoagulation.

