Study Endpoints	
In this Pilot study four domains of interest have been designated. The four domains are:
 
 • Patient Safety: Safety Endpoint Measures include adverse events, laboratory safety parameters, vital signs, EKG, ventilation status and hemodynamic variables. • Clinical Efficacy: The Primary Clinical Efficacy Endpoint Measure is in-hospital; 28 and 60-day all-cause mortality. Time to renal recovery and necessity for chronic dialysis up to day 60 will also be determined. Additional efficacy endpoints include time to intensive care unit (ICU) discharge, and time to hospital discharge. • Device Integrity and Performance: The Endpoint Measure is SCD use without failure. This measure will help assess the integrity and performance of the SCD device. • SCD Mode of Action: Exploratory Endpoint Measures will include inflammatory cytokines, cell activation parameters and biomarkers at clinical sites with this capability. The analysis will be performed at a central laboratory.
Assessment of Device Integrity and Performance	
Criteria for assessment of device integrity and performance include:
 
 • Significant Clotting within the Device as assessed by visual inspection. • Evidence of leakage (i.e., cracking/breakage of a port, connector, hemofilter cartridge or tubing).

	
 Any unforeseen malfunction that results in the need for discontinuation.
Study Populations	Pediatric patients with a body weight (BW) between ≥ 10 and ≤ 20 kg receiving care in the Intensive Care Units of each participating hospital will be screened daily and identified for participation in the trial.
Study Design	This is an open-label, multi-center Pilot study.
Approximate Number of Subjects	Up to 10 patients will be enrolled in this study.
Approximate Number of Centers	Up to 7 Clinical Centers in the United States will participate in this study.
Duration of Subject Participation	Each patient will be followed for 60 days following enrollment.

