1.2 RATIONALE FOR NUMBER OF SCD TREATMENTS FOR UP TO 10 DAYS

In prior studies, 10-35% of patients were still on CRRT at 7 days, including the recently completed SCD-PED-001 pediatric trial. Since the safety profile of the SCD in all the prior clinical studies have demonstrated no device related adverse events, the immunomodulatory effects on circulating white cells will maintain a beneficial response in a subject still requiring CRRT. The understanding of the mechanism of action of the SCD have demonstrated that the low iCa environment in the blood perfusion circuit initiates the natural apoptotic process of the bound neutrophils, thereby suppressing the excessive neutrophil inflammatory activity of the circulating innate immunologic system. The risk of neutropenia and immunosuppression is prevented due to this natural process. In addition, the treatment of four COVID-19 patients with the SCD under expanded access emergency use from 14-17 days had no SCD related adverse events.

In the recently completed SCD-PED-001 pediatric clinical trial, 5 of 14 patients required the full 7 day SCD treatment course, suggesting a subset of patients require more than 7 days of SCD treatment to recover and would benefit for longer duration of SCD treatment.

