2.4.2 SAFETY RESULTS

A summary of all adverse events (AEs) observed in the 35 subjects is presented in **Table 3**. The AEs observed were those expected for a critically ill patient population with acute renal failure and/or in an ICU setting.

Table 3. Summary of Adverse Events ARF-002

Adverse Events	Number of Subjects with Events N (% of 35)	Number of Events % of 199 (n/199)
Total adverse events	33 (94%)	199
Serious adverse event	23 (66%)	14.1% (28/199)
Unanticipated Adverse Device	0 (0%)	0.0% (0/199)
Relationship to Study*		
Unrelated to study therapy	32 (91%)	93.5% (186/199)
Possibly related to study therapy	8 (23%)	6.0% (12/199)
Probably related to study therapy	0 (0%)	0.0% (0/199)
Definitely related to study	1 (3%)	0.5% (1/199)
Outcome		
Resolved w/ sequelae	14 (40%)	13.6% (27/199)
Resolved w/out sequelae	25 (71%)	64.3% (128/199)
Continuing	11 (31%)	11.1% (22/199)
Death	11 (31%)	5.5% (11/199)
Reported as Unknown	3 (9%)	5.5% (11/199)
Frequency		
Single Episode	29 (83%)	54.3% (108/199)
Intermittent	16 (46%)	21.1% (42/199)
Continuous	16 (46%)	24.1% (48/199)
Reported as Unknown	1 (3%)	0.5% (1/199)

Adverse Events	Number of Subjects with Events N (% of 35)	Number of Events % of 199 (n/199)
Severity		
Mild	21 (60%)	34.7% (69/199)
Moderate	25 (71%)	51.8% (103/199)
Severe	19 (54%)	13.6% (27/199)

*Subjects experienced more than one AE, therefore, numbers do not add up to N=22 (number of subjects experiencing any adverse event).

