6.5 SCD TREATMENT PERIOD

The SCD Treatment Period begins when the subject starts treatment and will continue up to a maximum of 240 hours from the time of Treatment Start. A subject may begin CRRT therapy and SCD treatment at the same time, which would also mark the beginning of the SCD Treatment Period.

This treatment period has been broken into ten 24 hour time periods. It ends when the subject has reached 240 hours in the treatment period or when the subject meets the termination criteria outlined in **Section 7.2** as determined by the Principal Investigator or Medical Team at the participating Clinical Site.

All tests are scheduled on a 24 hour cycle, or once a day, and can be scheduled to be drawn around each participating site's ICU blood drawing schedule, with the exception of any test that requires a specific draw frequency.

The following information will be obtained for subjects enrolled during the SCD treatment period on a daily basis unless otherwise specified:

- **Vital Signs/Physical Assessment**
 - Temperature
 - Blood Pressure, heart rate
 - Urine Output (previous 24 hours)
 - Net Fluid Balance (previous 24 hours)
- **Clinical Laboratory Tests**
 - CBC with differential
 - BUN, Creatinine
 - Na, K, Cl, HCO₃, Ca, ionized Ca, Mg, PO₄
 - ALT, AST, Bilirubin, ALP, Total Protein, Albumin, Glucose
- **Respiratory**
 - Status – Ventilator support (yes/no; date of intubation or extubation, as applicable)
 - If on Vent: FiO₂
 - If on Vent with an arterial line: Arterial Blood Gas

- If on Vent without an arterial line: Arterial Blood Gas (if completed as standard of care)
- ECMO Status (yes/no; date of cannulation or decannulation as applicable)
- **Blood for Research**
 - Collect at hours 48, 96, 144, 192 and end of SCD treatment (\pm 6 hours). Blood for biomarkers will be collected as close as possible to the time of SCD scheduled changes in the days required (\pm 6 hours) if practical and within window.
 - Blood sample will be sent to an outside laboratory (Innovative Therapies) for testing of biomarkers
- **CRRT Parameters (Start at hour 0)**
 - Parameters include modality, blood flow rate, net fluid removal, dialysate or replacement solution flow rate, citrate infusion rate, calcium replacement rate.
 - System performance (circuit survival - event driven)
 - Post filter ionized calcium

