9.7. ADVERSE EVENT REPORTING

Adverse event reporting requirements will be based on the time period in which the adverse event occurs. It is understood that many of the signs and symptoms observed with ICU patients are expected. However, these should still be reported as adverse events if they meet the definitions of the Protocol. A “clinical care” event should therefore be reported as an adverse event if it meets any of the definitions. A group of symptoms that can be combined under one diagnosis, should be reported as a single adverse event. If a group of symptoms cannot be combined under one diagnosis, the symptoms should be reported as separate adverse events. These events will be reported as the number of events per time of exposure to the device.

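### Few children are expected to be treated past day 7 and no day 8-10 safety summary is planned, so the trial can say little about safety in days 8-10

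*Combined protocol and SAP*

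**What the plan says.** - **Objective.** Section 3.1: "To evaluate the safety of up to ten consecutive 24 hour SCD treatments compared to historic data on in-hospital mortality". Section 6.5 sets the ceiling: treatment "will continue up to a maximum of 240 hours from the time of Treatment Start".
- **Size.** Synopsis: "Up to 10 patients will be enrolled in this study". Sections 3.2 and 12 say the study is not powered.
- **Previous pediatric course.** Section 2.6: SCD-PED-001 treated for up to 7 days, in patients above 15 kg.
- **Case for extending.** Section 1.2: "In prior studies, 10-35% of patients were still on CRRT at 7 days, including the recently completed SCD-PED-001 pediatric trial". It adds that 5 of 14 patients in SCD-PED-001 used the whole 7-day course, and that four COVID-19 patients were treated for 14-17 days without SCD-related events. It also argues: "Since the safety profile of the SCD in all the prior clinical studies have demonstrated no device related adverse events".
- **Safety measure.** Section 9.7: "These events will be reported as the number of events per time of exposure to the device". No split by treatment day is given.
- **Related text.** Section 12 accepts that some minimum exposure is needed for a safety analysis but sets no number of children or days. It allows subset analysis in general terms, and the one subset it names is by ionized-calcium target. Section 11 puts the timing of adverse events within the DSMB's remit.
- **Earlier relatedness data.** Section 2.4.2, Table 3 (ARF-002) has a row "Possibly related to study therapy" with 12 events in 8 subjects, and 1 event classed as definitely related.

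**The concern.** In duration, what this trial adds to SCD-PED-001 is days 8 to 10. The SCD runs in series with the CRRT circuit, so a child who comes off CRRT before day 8 contributes nothing to that period. If few children reach it, and events are divided by total device time, the reported rate mostly describes the first week. A favourable overall rate could then be taken as support for ten completed treatments when little or no experience lies behind days 8-10. An event rate that rose late would also barely move the overall figure.

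The argument that might fill the gap, that earlier studies showed no device-related events, does not sit easily with Table 3.

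**Working it through.** The protocol gives no sample-size or precision calculation, so there is no design figure to reproduce. The check uses its own inputs.

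**Inputs.** N = 10 (Synopsis, Section 5.1). Probability p of treatment past day 7 = 0.10, 0.35 or 5/14 = 0.357 (Section 1.2). Ceiling of 10 days (Section 6.5). Assumption: children who pass day 7 complete day 10, and the others average m = 3 to 5 device-days. The protocol gives no mean.

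**1. Children expected past day 7 (N × p).** 10 × 0.10 = 1.0; 10 × 0.35 = 3.5; 10 × 5/14 = 3.6.

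**2. Spread (exact binomial, central 95%).** At p = 0.10: 0 to 3 children, with P(none) = 0.9^10 = 0.35. At p = 5/14: 1 to 7 children, with P(none) = (9/14)^10 = 0.012. Across both inputs the plausible range is 0 to 7.

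**3. Cross-check.** Section 12 reports 201 of 370 registry patients on CRRT for 1 to 7 days. The other 169 are not split into shorter and longer. If all 169 had gone beyond 7 days, the expected count would be 10 × 169/370 = 4.6.

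**4. Device-days in days 8-10 (3 × N × p).** 3 × 1.0 = 3.0; 3 × 3.57 = 10.7. These are expected values; 7 late children would give 21.

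**5. Share of device time.** Late days / [10 × late children + m × (10 − late children)].

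| Late children | m = 3 | m = 5 |
|---|---|---|
| 1.0 | 3/37 = 8.1% | 3/55 = 5.5% |
| 3.57 | 10.7/55.0 = 19.5% | 10.7/67.9 = 15.8% |

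If the true event rate doubled in days 8-10, the overall rate would rise by exactly this share. At m = 4 that is 3/46 = 7% with 1 late child and 10.7/61.4 = 17% with 3.57.

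**6. What a clean result would show.** For k children treated past day 7:

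| k | Zero events: one-sided 95% upper limit, 1 − 0.05^(1/k) | Chance of seeing at least one event at 20% true risk, 1 − 0.8^k |
|---|---|---|
| 1 | 95% | 20% |
| 3 | 63% | 49% |
| 4 | 53% | 59% |
| 10 (all exposed) | 26% | 89% |

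Even at the top of the plausible range, k = 7, the upper limit is 1 − 0.05^(1/7) = 35%.

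**7. Direction of error.** Being on CRRT at day 7, or using a full 7-day course, is not the same as continuing SCD into day 8. Section 7.2 also requires SCD to stop in children who do not reach the circuit calcium target in the first 12 hours, and enrolment may end below 10. The counts are therefore more likely high than low.

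**The case against.** The strongest reply is that the objective covers up to ten treatments in an unpowered pilot. Every enrolled child contributes to safety under a ten-day ceiling, and no section says the overall rate will be cited as proof that ten completed treatments are safe. That stands. A reader might infer that the trial cannot meet its primary objective; the documents do not support this.

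A reader might also infer that days 1-7 only repeat what SCD-PED-001 studied. They do not. That trial enrolled patients above 15 kg and this one enrols 10 to 20 kg, so the 10-15 kg band is new on every treatment day. Appendix E shows why weight matters: circuit volumes of 178 or 285 ml against an estimated blood volume of 700-1400 ml.

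Section 9.7 does not forbid rates by period, the DSMB looks at timing, and CBC is taken daily with hematologic stopping criteria for individual children in Section 7.2. A cytopenia would therefore be noticed during the trial. But these provisions concern monitoring, and none commits the final report to a day 8-10 summary.

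A reader might take Table 3 as refuting Section 1.2. That goes too far. Table 3 classifies relation to study therapy, which Section 7.3 of this protocol uses to mean CRRT plus SCD, and ARF-002's own definition is not shown. Table 3 also reports no unanticipated device events. The two passages are unreconciled, not shown to be contradictory.

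The four COVID-19 patients treated for 14-17 days are real longer exposure. They are outside this trial, and Section 1.2 gives neither their ages nor their weights.

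**Conclusion.** The concern holds as a matter of reporting and of how far conclusions can go. On the protocol's own figures, 1.0 to 3.6 children are expected past day 7 (plausibly 0 to 7). They would supply about 3 to 11 device-days in days 8-10, roughly 5-20% of device time. The share depends on the assumed 3-5 day average for the other children and on late children completing day 10; the counts do not. With 1 to 4 late children and no events, risks of 53% to 95% remain compatible with the data. The trial can describe safety under a ten-day maximum, including in the new weight band, but it can say little about days 8-10, and nothing in the plan would make that visible. This is not a case against the ten-day ceiling or for a larger trial.

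**What to change.** 1. In Section 9.7 and the safety analysis, tabulate adverse events, serious adverse events, CBC results and device failures separately for device days 1-7 and 8-10. Give children at risk, device-days at risk and exact intervals for each period.
2. In Section 3.1 or 12, state that conclusions about days 8-10 rest only on children treated beyond day 7 and are descriptive, and that the overall rate will not be cited as evidence for ten completed treatments.
3. In Section 1.2, reconcile the statement on device-related events with Table 3 (12 events possibly and 1 definitely related to study therapy). Either correct it or explain how device-related differs from study-therapy-related.

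**Cost.** Wording changes and one extra table split. No more patients or assessments are needed, because Sections 6.3 and 6.5 already collect these data by 24-hour period to hour 240. The late cells will be sparse, so the split will not itself establish safety in days 8-10, and the ten-day safety statement becomes more modest.

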3.1.1 SECONDARY OBJECTIVE

To assess the effect of SCD treatment on various measures of pediatric patient clinical outcome and to evaluate the integrity of the SCD device and patient safety in SCD treatments from the time of initiation of therapy to as many as ten consecutive 24-hour SCD treatments.

3.2 STUDY ENDPOINT

In this Pilot study four (4) domains of interest have been designated. The four (4) domains are:

1. Patient Safety: Safety Endpoint Measures include adverse events, laboratory safety parameters, vital signs, EKG, ventilation status and hemodynamic variables.
2. Clinical Efficacy: The Primary Clinical Efficacy Endpoint Measure is in-hospital; 28 and 60-day all-cause mortality. Time to renal recovery and necessity for chronic dialysis up to day 60 will also be determined. Additional efficacy endpoints include time to intensive care unit (ICU) discharge, and time to hospital discharge.
3. Device Integrity and Performance: The Endpoint Measure is SCD use without failure. This measure will help assess the integrity and performance of the SCD device.
4. SCD Mode of Action: Exploratory Endpoint Measures will include inflammatory cytokines, cell activation parameters and biomarkers at clinical sites with this capability.

Endpoints are defined as:

ALL-CAUSE MORTALITY:

All-cause mortality is defined as in-hospital, 28-day and 60-day all-cause mortality.

DIALYSIS DEPENDANCY AT DAY 60:

Dialysis dependency at day 60 is defined as patient not receiving any form of intermittent or continuous renal replacement therapy at or within 3 days of 60 days post enrollment in the study with no plans for additional intermittent or continuous renal replacement therapy.

PATIENT SAFETY:

Adverse events, laboratory safety parameters, vital signs, EKG, ventilation status and hemodynamic variables.

DURATION OF RENAL SUPPORT:

The duration of renal support will be defined as the numbers of days from the initiation of renal replacement therapy (start of observation period) to final dialysis treatment. Duration of renal support will be censored if the patient is still dialysis dependent at the time of death or are dependent at day 60.

RECOVERY OF RENAL FUNCTION:

Recovery of renal function will be defined as lack of need for continuous dialysis support on day 28, and will be classified as yes or no at day 28.

Subjects who were alive at day 28 will be included in the analysis.

Patients who remain dialysis dependent at study completion (day 60) or time of death will be categorized as having no recovery of renal function.

ASSESSMENT OF DEVICE INTEGRITY AND PERFORMANCE

Criteria for assessment of device integrity and performance include:

- Significant Clotting within the Device as assessed by visual inspection
- Evidence of leakage (i.e., cracking/breakage of a port, connector, hemofilter cartridge or tubing).
- Any unforeseen malfunction that results in the need for discontinuation.

This trial is an early safety efficacy study but is not powered for statistical significance. Insights into a comparison of historical controls matched to SCD treated subjects will utilize the ppCRRT Registry to match for: etiology of AKI, co-morbidities, CRRT modality, dose and form of anticoagulant, adverse events. [10]

The ppCRRT Registry has data fields for the primary reason for CRRT, including AKI and its cause, as well as co-morbidities which will be matched for primary organ system involvement. The CRRT modality was evenly distributed between convective and diffusive modality, with 60% of the convective modalities provided as CVVH and 40% as CVVHDF. The anticoagulant protocol will be standardized with ACD-A/CaCl₂ and all centers

used the same protocol in ppCRRT Registry as outlined in this study protocol. Thus, the ppCRRT Registry dataset will be able to be matched to our study subject cohort. Also as noted above, subjects will be matched for age, size and PRISM II score.

